## 8 STUDY ASSESSMENTS AND PROCEDURES

### 8.1 ENDPOINT AND OTHER NON-SAFETY ASSESSMENTS

*Primary outcomes.* The primary outcomes of the study are the obesogenic behaviors that are expected to change as a result of participation in the intervention including:

- Diet: Within diet, we are interested in both healthy eating (e.g., fruits and vegetables, whole grain, fiber, calcium) and unhealthy eating (sugary and salty foods, fast foods, sugar-sweetened beverages, saturated fats) (healthy and unhealthy). The Dietary Screener Questionnaire and National Youth Physical Activity and Nutrition Study survey, two measures widely used in diet and obesity-related research with acceptable reliability and validity will be used to assess diet. These questionnaires assess frequency of intake in the past 7-30 days.
- Activity: Both physical activity and sedentary activity will be assessed. The Youth Activity Profile is a 15-item questionnaire designed to assess physical activity and sedentary behavior in youth. This self-report measure has been cross-validated with objective measures of physical activity and resulted in similar group estimates acquired from objective measures. The Godin and Shephard Leisure-Time Physical Activity Questionnaire is a 3-item self-report assessment of leisure time physical activity and provides corresponding metabolic equivalents. Both measures provide minutes in activity and use a 7-day recall.

*Secondary outcomes.* The secondary outcomes of the study is change in health literacy.

- Four types of health literacy will be assessed. Functional, interactive, and critical health literacy will be assessed using an objective measure, the Adolescent Assessments of Health Literacy. Media health literacy will be measured using an objective measure, Adolescent Media Health Literacy Scale.

All assessments are validated and will be scored per the test authors' scoring guidelines.

### 8.2 ADVERSE EVENTS AND SERIOUS ADVERSE EVENTS

#### 8.2.1 DEFINITION OF ADVERSE EVENTS

This protocol uses the definition of adverse event from 21 CFR 312.32 (a): any untoward medical occurrence associated with the use of an intervention in humans, ***whether or not considered intervention-related***.

#### 8.2.2 DEFINITION OF SERIOUS ADVERSE EVENTS

An adverse event is serious when medical or surgical intervention is required to prevent any of the following, or when any of the following occur:

- o Death
- o A life-threatening situation
- o Inpatient hospitalization
- o Prolongation of existing hospitalization

o A persistent or significant disability/incapacity, or congenital anomaly/birth defect

---

### 8.2.3 CLASSIFICATION OF AN ADVERSE EVENT

---

#### 8.2.3.1 SEVERITY OF EVENT

For adverse events (AEs) not included in the protocol defined grading system, the following guidelines will be used to describe severity.

- **Mild** – Events require minimal or no treatment and do not interfere with the participant’s daily activities.
- **Moderate** – Events result in a low level of inconvenience or concern with the therapeutic measures. Moderate events may cause some interference with functioning.
- **Severe** – Events interrupt a participant’s usual daily activity and may require systemic drug therapy or other treatment. Severe events are usually potentially life-threatening or incapacitating. Of note, the term “severe” does not necessarily equate to “serious”.

---

#### 8.2.3.2 RELATIONSHIP TO STUDY INTERVENTION/EXPERIMENTAL MANIPULATION

All adverse events (AEs) will have their relationship to study procedures, including the intervention, assessed by an appropriately-trained clinician based on temporal relationship and his/her clinical judgment. The degree of certainty about causality will be graded using the categories below.

- **Related** – The AE is known to occur with the study procedures, there is a reasonable possibility that the study procedures caused the AE, or there is a temporal relationship between the study procedures and the event. Reasonable possibility means that there is evidence to suggest a causal relationship between the study procedures and the AE.
- **Not Related** – There is not a reasonable possibility that the study procedures caused the event, there is no temporal relationship between the study procedures and event onset, or an alternate etiology has been established.

OR

- **Definitely Related** – There is clear evidence to suggest a causal relationship, and other possible contributing factors can be ruled out. The clinical event, including an abnormal laboratory test result, occurs in a plausible time relationship to study procedures administration and cannot be explained by concurrent disease or other drugs or chemicals. The response to withdrawal of the

study procedures should be clinically plausible. The event must be pharmacologically or phenomenologically definitive.

- **Probably Related** – There is evidence to suggest a causal relationship, and the influence of other factors is unlikely. The clinical event, including an abnormal laboratory test result, occurs within a reasonable time after administration of the study procedures, is unlikely to be attributed to concurrent disease or other drugs or chemicals, and follows a clinically reasonable response on withdrawal.
- **Potentially Related** – There is some evidence to suggest a causal relationship (e.g., the event occurred within a reasonable time after administration of study procedures). However, other factors may have contributed to the event (e.g., the participant’s clinical condition, other concomitant events). Although an AE may rate only as “possibly related” soon after discovery, it can be flagged as requiring more information and later be upgraded to “probably related” or “definitely related”, as appropriate.
- **Unlikely to be related** – A clinical event, including an abnormal laboratory test result, whose temporal relationship to study procedures administration makes a causal relationship improbable (e.g., the event did not occur within a reasonable time after administration of the study procedures) and in which other drugs or chemicals or underlying disease provides plausible explanations (e.g., the participant’s clinical condition, other concomitant treatments).
- **Not Related** – The AE is completely independent of study procedures administration, and/or evidence exists that the event is definitely related to another etiology. There must be an alternative, definitive etiology documented by the clinician.

---

#### 8.2.3.3 EXPECTEDNESS

A clinician with appropriate expertise in pediatric psychology or pediatrics will be responsible for determining whether an adverse event (AE) is expected or unexpected. An AE will be considered unexpected if the nature, severity, or frequency of the event is not consistent with the risk information previously described for the study procedures.

---

#### 8.2.4 TIME PERIOD AND FREQUENCY FOR EVENT ASSESSMENT AND FOLLOW-UP

The occurrence of an adverse event (AE) or serious adverse event (SAE) may come to the attention of study personnel during study visits and interviews of a study participant presenting for medical care, or upon review by a study monitor.

All AEs, not otherwise precluded per the protocol, will be captured on the appropriate case report form (CRF). Information to be collected includes event description, time of onset, clinician’s assessment of severity, relationship to study procedures (assessed only by those with the training and authority to make a diagnosis), and time of resolution/stabilization of the event. All AEs occurring while on study will be documented appropriately regardless of relationship. All AEs will be followed to adequate resolution.

Any medical or psychiatric condition that is present at the time that the participant is screened will be considered as baseline and not reported as an AE. However, if the study participant's condition deteriorates at any time during the study, it will be recorded as an AE.

Changes in the severity of an AE will be documented to allow an assessment of the duration of the event at each level of severity to be performed. Documentation of onset and duration of each episode will be maintained for AEs characterized as intermittent.

The PI will record events with start dates occurring any time after informed consent is obtained until 7 (for non-serious AEs) or 30 days (for SAEs) after the last day of study participation. At each study visit, the investigator will inquire about the occurrence of AE/SAEs since the last visit. Events will be followed for outcome information until resolution or stabilization

---

#### 8.2.5 ADVERSE EVENT REPORTING

Although the intervention in this clinical trial poses low risk to participants, adverse events information will be collected at all assessments as part of the study protocol and participants will be advised to use the "contact research staff" button to report any adverse experiences during the course of the intervention. Adverse events will be recorded on forms that are consistent with NIH and the CUNY University Integrated IRB policies. While we do not expect this research to result in adverse events that lead to a participant seeking medical care and/or hospitalization, if this should occur, then they will be reported by the PI to the IRB within 24 hours and on annual reports to the IRB. Additional reporting to the project officer at NIH will be carried out within 7 days of the incident. Study activities will also be suspended until determination of risk to other participants is made by the IRB.

---

#### 8.2.6 SERIOUS ADVERSE EVENT REPORTING

In consultation with the PI, a trained member of the study team will be responsible for conducting an evaluation of a serious adverse event and shall report the results of such evaluation to the NIH and the reviewing Institutional Review Board (IRB) as soon as possible, but in no event later than 10 working days after the investigator first learns of the event.

---

### 8.3 UNANTICIPATED PROBLEMS

---

#### 8.3.1 DEFINITION OF UNANTICIPATED PROBLEMS

This protocol uses the definition of Unanticipated Problems as defined by the Office for Human Research Protections (OHRP). OHRP considers unanticipated problems involving risks to participants or others to include, in general, any incident, experience, or outcome that meets all of the following criteria:

- Unexpected in terms of nature, severity, or frequency given (a) the research procedures that are described in the protocol-related documents, such as the Institutional Review Board (IRB)-

approved research protocol and informed consent document; and (b) the characteristics of the participant population being studied;

- Related or possibly related to participation in the research ("possibly related" means there is a reasonable possibility that the incident, experience, or outcome may have been caused by the procedures involved in the research); and
- Suggests that the research places participants or others at a greater risk of harm (including physical, psychological, economic, or social harm) than was previously known or recognized.

---

### 8.3.2 UNANTICIPATED PROBLEMS REPORTING

The investigator will report unanticipated problems (UPs) to the reviewing Institutional Review Board (IRB). The UP report will include the following information:

- Protocol identifying information: protocol title and number, PI's name, and the IRB project number
- A detailed description of the event, incident, experience, or outcome
- An explanation of the basis for determining that the event, incident, experience, or outcome represents an UP
- A description of any changes to the protocol or other corrective actions that have been taken or are proposed in response to the UP

To satisfy the requirement for prompt reporting, UPs will be reported using the following timeline:

- UPs that are serious adverse events (SAEs) will be reported to the IRB and to the study sponsor/funding agency within 10 days of the investigator becoming aware of the event
- Any other UP will be reported to the IRB and to the study sponsor/funding agency within 10 of the investigator becoming aware of the problem
- All UPs should be reported to appropriate institutional officials (as required by an institution's written reporting procedures), the supporting agency head (or designee), and the Office for Human Research Protections (OHRP) within 30 days of the IRB's receipt of the report of the problem from the investigator

## 9 STATISTICAL CONSIDERATIONS

### 9.1 STATISTICAL HYPOTHESES

- Primary Efficacy Endpoint(s):

Adolescents in the experimental condition (obesity prevention plus health literacy) will have higher rates of obesity prevention behaviors at follow-up compared to the obesity prevention only group.

### 9.2 SAMPLE SIZE DETERMINATION

This is a feasibility pilot study, therefore the sample size was not determined via power calculations.

### 9.3 POPULATIONS FOR ANALYSES

Intention-to-Treat (ITT) analysis population (i.e., all randomized participants).

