## 1 PROTOCOL SUMMARY

### 1.1 SYNOPSIS

Title:	Health Literacy and Obesogenic Behaviors
Grant Number:	R21DK117345
Study Description:	The goal of the proposed study is to examine the effect of adding a health literacy component to an obesity prevention intervention that addresses adolescents' obesogenic behavior-related health knowledge, motivation, and behavioral skills. The central hypothesis is adolescents receiving health literacy training as part of an obesity prevention intervention will have higher rates of prevention behaviors than those in the obesity prevention only condition.
Objectives*:	Primary Objective: Determine if the addition of HL training to an interactive digital obesity prevention intervention will improve adolescents' obesity prevention behaviors over the obesity intervention alone.
Endpoints*:	Primary Endpoint: 1-month follow-up
Study Population:	Adolescents
Phase* or Stage:	Phase 1
Description of Sites/Facilities Enrolling Participants:	Community sites in the United States
Description of Study Intervention/Experimental Manipulation:	Web-based intervention administered to individuals. The intervention contains 5 modules with an expected completion rate of 1 module per week.
Study Duration*:	5 months
Participant Duration:	3 months

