### 1.2 SCHEDULE OF ACTIVITIES

	Week 1	Week 2	Weeks 3-7	Week 8	Week 12
Parent permission	X				
Adolescent assent		X			
Pretest survey including all		X			

outcome  
measures

Randomization		X			
Control & experimental interventions			X		
Posttest survey				X	
1-month follow- up survey					X
Adverse event reporting	X	X	X	X	X

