#### 4.4 END-OF-STUDY DEFINITION

A participant is considered to have completed the study if he or she has completed the pretest assessments, all intervention modules, posttest assessments, and 1-month follow-up assessments. The end of the study is defined as completion of the 1-month follow-up assessment.

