#### Retention

One of the advantages of a digital intervention is that it decreases the travel and time burdens as individuals may complete the modules based on their individual schedules. While adolescents may not prioritize the intervention or forget about it given the lack of deadline, the intervention will have a built-in point system to immediately incentivize data collection and module completion. For example, participants will be provided with a suggested schedule for completing the modules and will receive email and text prompts encouraging them to log in and complete the module prior to the scheduled date. They will be incentivized through the point system for completing the module early and according

to the schedule. Participants will also be incentivized through the point system to complete each module in one sitting to facilitate making connections across the module. Though participants will receive gift cards at each data collection completion, they will also receive points for completing data collections. These points may be redeemed for prizes at the end of the study through the points store where more desirable prizes will require more points. Collecting biometric data at posttest and follow-up may be difficult given that all other data collection will occur online. Bonus incentives for completing all aspects of the study (intervention and all data collection) should further motivate participants to maintain involvement in the project. The use of email and text prompts throughout the study should also encourage retention. We plan to collect multiple phone numbers and email address for participants and their parents to be able to reach them in the event of lost devices or changes in phone numbers or email addresses.

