### 9.4 STATISTICAL ANALYSES

#### 9.4.1 GENERAL APPROACH

Descriptive analyses will be calculated for all variables. We will compare the two study groups on baseline variables to assess whether balance was achieved through the randomization. Changes from pretest to 1-month follow-up on continuous primary and secondary outcome variables will be compared between groups using t-tests. Binary primary and secondary outcome variables (outcome improved vs. not improved) will be compared between groups using Chi-tests.

Group differences on change in physical activity (i.e., metabolic equivalents, number of days 60 minutes or more of physical activity), and diet (number of fruits and vegetables, junk food, sugar-sweetened beverages consumed per week), as well as the standard deviations of the changes in each group, will be used to calculate sample size for the next study.

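### Section 9.3 declares an ITT set of all randomized participants, but the change-score t-test in 9.4.1, with no missing-data method, in effect analyses only those with both surveys

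*Combined protocol and SAP*

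**What the plan says.** Section 9.3 defines a single analysis set: "Intention-to-Treat (ITT) analysis population (i.e., all randomized participants". The synopsis (1.1) fixes the time point: "Primary Endpoint: 1-month follow-up".

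Section 9.4.1 gives two tests. For continuous outcomes: "Changes from pretest to 1-month follow-up on continuous primary and secondary outcome variables will be compared between groups using t-tests". For binary outcomes: "Binary primary and secondary outcome variables (outcome improved vs. not improved) will be compared between groups using Chi-tests". It names no imputation, no repeated-measures model, no rule for a missing follow-up and no sensitivity analysis.

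The schedule (1.2) places a "Posttest survey" at week 8, between the pretest at week 2 and the follow-up at week 12. Section 4.4 counts a participant as a study completer only after having "completed the pretest assessments, all intervention modules, posttest assessments, and 1-month follow-up assessments". The posttest appears in neither test in 9.4.1. The only analysis that could cover it is the general statement "Descriptive analyses will be calculated for all variables".

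Three passages bear on who will have week-12 data:

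- 7.1 ends the remaining study procedures for a participant who discontinues the intervention.
- 7.2 lets an investigator remove a participant for marked non-compliance.
- 7.3 classes unreachable participants as withdrawn.

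**The concern.** The population in 9.3 and the test in 9.4.1 do not fit together once anyone lacks the week-12 survey. A t-test on change leaves those participants out, yet the result would be reported as ITT.

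The loss is unlikely to be unrelated to outcome. All three routes in section 7 depend on engagement. Engagement could differ by arm, because module 2 differs (vaping or health literacy, 6.1.1) and there is no masking (6.3).

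As this is a pilot, the main harm lies downstream. Sections 4.2 and 9.4.1 use the group differences and the SDs of change to size the next trial, so a distortion from selective dropout would be carried into that calculation.

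**Working it through.** **No figure to reproduce.** The documents state no N, alpha, power, effect size, SD, dropout rate or correlation. All numerical inputs below are assumptions, used for scale only. Bias is in SD units of a single survey measurement.

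**1. Who is analysed.** With dropout d, the t-test uses N × (1 − d) participants. For an assumed 60 randomized:

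| d | analysed | left out |
|---|---|---|
| 10% | 54 | 6 |
| 20% | 48 | 12 |
| 30% | 42 | 18 |
| 40% | 36 | 24 |

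**2. Selection on a week-8 measure.** Suppose that in one arm 40% of those below the week-8 median drop out, against 20% of those above, and that dropout in the other arm is random. The mean of a standard normal above its median is 0.798. The completers' mean on the selecting measure is [0.5 × 0.6 × (−0.798) + 0.5 × 0.8 × 0.798] / 0.7 = 0.114 SD.

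**3. From there to the tested quantity, the change at week 12.** Take a week-8 to week-12 correlation of 0.6, and let r be the correlation of pretest with each later survey.

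- Dropout follows the week-8 *level*: bias = 0.114 × (0.6 − r).
- Dropout follows the week-8 *change*: bias = 0.114 × (0.6 − 2r + 1) / √(2(1 − r)).

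| r | follows level | follows change |
|---|---|---|
| 0.4 | 0.114 × 0.2 = 0.02 | 0.114 × 0.8 / 1.095 = 0.08 |
| 0.5 | 0.114 × 0.1 = 0.01 | 0.114 × 0.6 / 1 = 0.07 |
| 0.6 | 0 | 0.114 × 0.4 / 0.894 = 0.05 |

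Selection on level partly cancels, because completers are then shifted upward at pretest as well as at week 12.

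**4. Simulation.** There were 4,000 runs per setting, with no true effect, SD 1, correlations of 0.5 (pretest with posttest and with 1 month) and 0.7 (posttest with 1 month), and 30 or 100 per arm. Dropout was 10 to 40% and equal in both arms. It depended on posttest level (log-odds slope 1) in one arm and was random in the other.

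- The completers' change-score estimate was biased by 0.013 to 0.075, rising with dropout.
- A regression estimate that used an observed posttest had bias within 0.004 of zero.
- If the posttest was missing too, an estimate using pretest alone had bias of 0.037 to 0.165, more than the change-score estimate in the same settings.
- The t-test rejected a true null at the 5% level in 4.6 to 6.5% of runs.

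**5. Which participants have a posttest.** The interventions run in weeks 3 to 7 and the posttest is at week 8. Read literally, 7.1 leaves a participant who stops during the intervention with neither posttest nor 1-month data. Week 8 is informative only for those who gave it and then missed week 12.

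**The case against.** The plan is silent on missing data; it does not prescribe a complete-case analysis. If every randomized adolescent completed week 12, the two sets would coincide. That is true, but sections 7.1 to 7.3 make it unlikely, and a change-score t-test with no missing-data rule has no other way to proceed.

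The retention text in section 5.4 does say "While adolescents may not prioritize the intervention or forget about it given the lack of deadline". The same sentence goes on to the point system, and gift cards, bonus incentives, reminders and multiple contacts follow. The clause also concerns the programme rather than the week-12 survey. It is weak evidence of missing surveys, and section 7 carries the argument better.

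A reader might infer that the posttest is never used. The documents support only the narrower statement that it enters no test between arms, since the descriptive analyses may include it. Nor does omitting it make the analysis complete-case; the absence of a missing-data method does.

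A reader might also infer that the week-8 data already collected would remove the bias. Under 7.1 that fails for those who stop the intervention before week 8, and step 4 shows that a model left with pretest alone can do worse than the t-test.

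Finally, this is a feasibility pilot without a power calculation (9.2), and section 10.1.4 calls the sample small. That argues for a modest model. It does not justify an ITT label on a completers' analysis.

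**Conclusion.** The concern holds in this form: the declared population and the stated continuous-outcome test disagree whenever 1-month data are missing, and the plan offers nothing to bridge them. The binary comparison could include everyone if a missing follow-up had a stated value, but none is given.

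The size of any bias is unknown. With 40% against 20% dropout around the week-8 median in one arm, it is about 0 to 0.02 SD if dropout follows the week-8 level. It is about 0.07 SD (0.05 to 0.08 for r from 0.6 to 0.4) if dropout follows the week-8 change. The simulation shows that level-driven dropout can also reach about 0.07 SD when dropout is heavy and the correlations differ more. In that simulation, false positives rose little, so the issue is a shifted estimate and a misnamed population rather than an invalid test.

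A reader might double 0.07 to 0.14 SD by assuming opposite dropout patterns in the two arms. Nothing in the documents points to that, and the arms share four of five modules.

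**What to change.** In 9.4.1, replace the change-score t-test with a baseline-constrained repeated-measures model: pretest, posttest and 1-month values as outcomes, a common pretest mean, arm by visit, and the 1-month arm contrast as primary. State a simpler covariance structure to use if the sample is small. Include every randomized participant with at least one survey, in the arm assigned. A model with pretest only as a covariate would drop those who have nothing after pretest, so it does not meet 9.3.

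Also:

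- State how a missing follow-up is counted in the improved/not improved comparison.
- Report missingness at each survey by arm.
- Add one sensitivity analysis that shifts missing week-12 values over a range fixed in advance.
- Reconcile 7.1 with the ITT definition in 9.3. If they are not reconciled, label the analysed set as completers.

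The model needs only SAP wording, standard software and data already scheduled. Its downside is slightly more modelling than a t-test. Reconciling 7.1 with 9.3 is a protocol matter and may cost more than a wording change. The model does not by itself cover participants who have only a pretest; for them the sensitivity analysis carries the weight.
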